8.2. Study Drug Dispensing

Study drug will be dispensed to subjects on study Days 2, 8 and 15 as indicated in the schedule of assessments (refer to [Appendix A](#)). Each daily dose will be dispensed into separate containers and provided to the subject at the study site.

If a dose reduction is required subjects must return to the study site for study drug to be re-dispensed. Subjects must return any remaining study drug and all study drug containers to the site where they will be destroyed as instructed by the Sponsor.

8.3. Dose Modification

Modification of study drug dosing may be considered if, in the opinion of the study Investigator, the AE may be related to study drug and it would be unsafe for the subject to continue receiving their current dose of study drug. The Investigator's assessment of AE relatedness should take into account the toxicity profile of all concomitant medications including pirfenidone and nintedanib.

Not all AEs require study drug modifications and may be managed as determined by the Investigator.

The Sponsor's Medical Director should be contacted prior to any change in dosing.

8.3.1. Dose Adjustment

Dose adjustments may be initiated by the Investigator based on their assessment of the associated AE severity and overall subject safety and in discussion with the Sponsor's Medical Director.

The Investigator, in discussion with the Sponsor's Medical Director, may choose to:

- Change dosing frequency, to one capsule 3 times per day
- Reduce the total daily dose

A reduction in dose should be by one active study drug capsule. Dose reductions will require the subject to return to the study site for the unblinded pharmacist to dispense new study drug capsules. Subjects will continue to take 3 capsules per day if in Part A and 5 capsules per day if in Part B of the study.

A second dose reduction by another one active study drug capsule may be initiated if deemed necessary by the Investigator and based on a safety assessment of the subject. The timing of the second dose reduction will be based on the Investigator's clinical assessment and in discussion with the Sponsor's Medical Director.

The Investigator must make every effort to restart the dosing regimen assigned to the subject at randomization, as soon as it is safe to do so.

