1.5.3. Dose Rationale

The selection of GBT440 doses for investigation in IPF patients is based on pharmacodynamic (PD) targets that are expected to correspond to an increase in Hb-O₂ affinity which may result in a clinically significant increase in oxygenation. These PD targets are derived from data from three nonclinical pharmacology studies that included a hypoxia challenge model and two models of pulmonary hypoxemia (refer to the IB for details of these studies). Based on the in vivo data the lower limit for treatment response during exercise-induced desaturation is expected to be ~20% Hb occupancy by GBT440.

The dose levels predicted to achieve the Hb modification targets of ~20% to ~50% in IPF subjects are based on clinical PK and PD data from study GBT440-001. Dose levels of 600 mg or 900 mg per day administered to healthy subjects for 15 days resulted in a mean Hb modifications of 24% and 38%, respectively. A dose level of 300 mg per day resulted in a mean Hb modification of 11%, which is below the PD effect that showed benefit in animal models of hypoxemia.

The safety of the proposed doses of 600 mg and 900 mg in the initial cohort (Part A) of approximately 18 subjects and the safety of pursuing parallel dosing in this study are based on the totality of available nonclinical and clinical safety data. The expansion Cohort (Part B) of 15 subjects will have 3 dose arms: 1500 mg, 600 mg and placebo. Addition of a higher dose is supported by: the acceptable safety profile collected from the Part A subjects dosed to date in this study; review by the Safety Monitoring Committee of safety data from 12 subjects who completed up to 28 days and 16 subjects who completed 15 days of dosing in Part A and Safety Monitoring Committee agreement to proceed with the evaluation of GBT440 1500 mg; continued favorable safety profile in ongoing studies evaluating GBT440 in subjects with SCD, including continued dosing for up to 6 months; and an anticipated dose-dependent improvement in oxygen saturation. Guidelines for the safety review of Part A and Part B of the trial are outlined in the Safety Monitoring Committee section ([Section 10.1](#)).

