8. DOSAGE AND TREATMENT ADMINISTRATION

8.1. Treatment Regimen

GBT440 and placebo will be administered orally each day for 28 days. GBT440 will be administered as 300 mg capsules. Placebo will be provided as capsules matching the GBT440 capsules. Subjects randomized to the following treatment groups will receive:

Part A:

- GBT440 900 mg: 3 GBT440 300 mg capsules.
- GBT440 600 mg: 2 GBT440 300 mg capsules and 1 placebo capsule.
- Placebo: 3 placebo capsules.

Part B:

- GBT440 1500 mg: 5 GBT440 300 mg capsules
- GBT440 600 mg: 2 GBT440 300 mg capsules and 3 placebo capsule.
- Placebo: 5 placebo capsules.

Instructions for Administration of Study Drug:

- Self-administered by subject in the morning
 - except on study visit days when the subject must not take study drug. It will be administered at the site after completion of scheduled assessments.
- May be taken with or without food
- May be taken with water or other non-alcoholic beverage

Subjects must be instructed not to take study drug the day of their scheduled visits (refer to [Appendix A](#)). Study drug will be administered at the site on these days, after completion of all the assessments scheduled for that visit.

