13. ADMINISTRATIVE OBLIGATIONS

13.1. Source Data

Original documents, data, records (e.g., clinic records, laboratory notes, memoranda, subject diaries or evaluation checklists, pharmacy dispensing records, recorded data from automated instruments, copies or transcriptions certified after verification as being accurate and complete, microfiches, photographic negatives, microfilm or magnetic media, X-rays, subject files, and records kept at the pharmacy, at the laboratories, and at medico-technical departments involved in the clinical trial) and all relevant sections of the subject's medical records and all other data collection made specific to this trial constitute source documents.

The completed CRF is not a source document. The Investigator/institution will permit trial-related monitoring, audits, IRB review and regulatory inspection by providing direct access to source documents.

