- ^m PK blood samples during the treatment period should be collected on Days 1 and 28: pre-dose, and 2 hours post dose (+/- 15 minutes); Day 2: 24 hours (+/- 2 hours) after the Day-1 dose *and* prior to receiving the Day-2 dose; Days 8 & 15: pre-dose only. Also see Protocol Section 5.6.
- ⁿ Instructions for per-protocol performance of the 6-minute walk (and Borg dyspnea scale) and cardio-pulmonary exercise tests are provided in the procedure manual. Note: The baseline 6MWT performed during screening must be performed within 7 days of the Day-1 visit.
- ^o An unblinded study pharmacist will prepare daily doses of study drug, dispensed into 30 mL high-density polyethylene (HDPE) bottles. Each bottle (or dose) is packaged individually with 3 capsules of active or placebo or both specific to each subject’s assigned treatment group. Subjects who have their dose modified during the study must return to the site to have the modified dose of study drug dispensed by the unblinded pharmacist.
- ^p Subjects should not administer study drug on the morning of these study visits. Study drug will be administered by the study staff after completion of all pre-dose assessments.
- ^q The SGRQ, ATAQ, and UCSD questionnaires and cough VAS should be self-administered by the subject, using the paper forms provided by the Sponsor prior to all other non-PRO assessments and before the patient receives any disease-status information during that assessment. ATAQ questionnaires should be administered to subjects enrolled in Part b of the study.
- ^r The End of Study Questionnaire should be administered to subjects enrolled in Part B of the study.

6. Study Treatments

The study drug is GBT440 300 mg capsules or placebo.

Subjects randomized to the following treatment groups in Part A will receive:

- GBT440 900 mg -- 3 GBT440 300 mg capsules
- GBT440 600 mg -- 2 GBT440 300 mg capsules and 1 placebo capsule.
- Placebo -- 3 placebo capsules.

Subjects randomized to the following treatment groups in Part B will receive:

- GBT440 1500 mg -- 5 GBT440 300 mg capsules
- GBT440 600 mg -- 2 GBT440 300 mg capsules and 3 placebo capsules.
- Placebo -- 5 placebo capsules.

Study drug is to be dosed orally once daily for a total of 28 days.

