6.2 Dose Modifications and Adjustments

Modification of study drug dosing may be considered if, in the opinion of the study Investigator, an AE may be related to study drug and it would be unsafe for the subject to continue receiving their current dose of study drug.

Dose adjustments may be initiated by the Investigator based on their assessment of the associated AE severity and overall subject safety and in discussion with the Sponsor's Medical Director.

The Investigator, in discussion with the Sponsor's Medical Director, may choose to:

- Change dosing frequency, to one capsule 3 times per day
- Reduce the total daily dose

A reduction in dose should be by one active study drug capsule. Dose reductions will require the subject to return to the study site for the unblinded pharmacist to dispense new study drug capsules. Subjects in Part A will continue to take 3 capsules per day. Subjects in Part B will continue to take 5 capsules per day.

A second dose reduction by one active study drug capsule may be initiated if deemed necessary by the Investigator and based on a safety assessment of the subject. The timing of the second dose reduction will be based on the Investigator's clinical assessment and in discussion with the Sponsor's Medical Director.

The Investigator must make every effort to restart the dosing regimen assigned to the subject at randomization when, in the investigator's opinion, it is safe to do so.

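### A second dose reduction in the 600 mg arm leaves 0 mg of GBT440, and SAP 14.2 still counts those placebo-only days as exposure

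*Protocol*

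**What the plan says.** Protocol 8.3.1 sets each reduction at one active capsule and then adds: "A second dose reduction by another one active study drug capsule may be initiated if deemed necessary by the Investigator". SAP 6.2 carries the same rule: "A second dose reduction by one active study drug capsule may be initiated if deemed necessary by the Investigator". Neither section sets a minimum dose or makes an exception for any arm. The number of capsules taken does not fall: "Subjects will continue to take 3 capsules per day if in Part A and 5 capsules per day if in Part B of the study". Each removed active capsule is therefore replaced by placebo.

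Protocol 8.1 gives the Part A low-dose regimen as "GBT440 600 mg: 2 GBT440 300 mg capsules and 1 placebo capsule". The Part B low-dose regimen also has two active capsules, with three placebo capsules.

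SAP section 6 states: "The study drug is GBT440 300 mg capsules or placebo". SAP 14.2 measures exposure as the days from first to last dose, less missed doses and interruption days. SAP 14.3 divides days dosed by the days from first to last dose. SAP 9.2 admits to the Efficacy-Evaluable population any randomized subject with at least 14 days of study drug. SAP section 19 gives the reason for 14: it is half of the 28-day course.

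**The concern.** The reduction rule works as intended in the two higher-dose arms but reaches zero in the 600 mg arm. A subject there can still be swallowing three or five capsules a day while receiving no GBT440. Study drug includes placebo by definition, and a reduction is neither a missed dose nor an interruption. Nothing in SAP 14.2 or 14.3 removes such days.

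Two summaries could then mislead. The 600 mg exposure figure, which is the context for reading tolerability at that dose, would include days without drug. A subject could also meet the 14-day Efficacy-Evaluable criterion partly on placebo, and that subject's walk-test SpO₂ would enter the comparisons of 600 mg and of all GBT440 with placebo in SAP section 16. Protocol 6.3 treats a visit two weeks after the last dose as at least 5 half-lives later. A subject whose last active capsule was on Day 13 would be 28 − 13 = 15 days off GBT440 at the Day 28 test.

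**Working it through.** **Inputs.** Capsules are 300 mg (Protocol 8.1). Active capsules per day are 5, 3 and 2 in the 1500, 900 and 600 mg arms (Protocol 8.1). One reduction removes one active capsule, and two are allowed (Protocol 8.3.1, SAP 6.2). Treatment lasts 28 days (SAP section 6). Planned 600 mg subjects are 6 in Part A and 3 in Part B, pooled under SAP 10.3, so n = 9. All reduction and restoration dates below are assumptions.

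**Step 1: daily dose after k reductions** = (active capsules − k) × 300 mg.

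| Arm | k = 0 | k = 1 | k = 2 |
|---|---|---|---|
| 1500 mg | 1500 | 1200 | 900 |
| 900 mg | 900 | 600 | 300 |
| 600 mg | 600 | 300 | **0** |

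The k = 0 column reproduces the assigned doses. Only the 600 mg arm reaches zero.

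**Step 2: a 0 mg week, later restored.** Reduced to 300 mg on Day 8 and to 0 mg on Day 15, restored to 600 mg on Day 22, no capsules missed.

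- Planned amount: 28 × 600 = 16,800 mg.
- Amount received: 7 × 600 + 7 × 300 + 7 × 0 + 7 × 600 = 10,500 mg, or 62.5%.
- Days with any GBT440: 28 − 7 = 21.
- SAP 14.2 exposure, recorded as a reduction: (28 − 1) + 1 − (0 + 0) = 28 days.
- SAP 14.3 compliance, recorded as a reduction: 28/28 = 100%.
- The same week taken as an interruption, exposure: (28 − 1) + 1 − (0 + 7) = 21 days.
- The same week taken as an interruption, compliance: 21/28 = 75%.

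GBT440 intake is identical on the two routes; the reported figures are not.

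**Step 3: effect on the arm mean.** If the other 8 subjects have 28 days each, the mean by SAP 14.2 is 28.00. With active days for this one subject it is (8 × 28 + 21)/9 = 27.22. The difference is 7/9 = 0.8 days.

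**Step 4: Efficacy-Evaluable status without restoration.** If the second reduction takes effect on Day d, active days = d − 1. For d = 14 this is 13; for d = 15 it is 14. Provided capsules are still taken for at least 14 days, the subject qualifies with fewer than 14 active days only when d ≤ 14. The Step 2 subject, with 21 active days, qualifies on either count.

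**The case against.** The best defence is that counting capsule-days is a coherent convention. It treats every arm alike, placebo included, and the fixed capsule count protects the blind. The information is also largely available elsewhere. SAP 14.1 tabulates subjects by number of reductions, SAP 10.3 and 14.3 list dosing by subject, and Protocol 5.6 measures drug concentrations on Days 8, 15 and 28. With 9 planned subjects, two reductions in the 600 mg arm would identify every possible case. Protocol 8.3 adds that the Sponsor's "Medical Director should be contacted prior to any change in dosing", and in Part B the Sponsor is unblinded. The Study Drug CRF and pharmacy manual are not among the documents and may cover part of this. The study has no formal hypotheses (SAP 3.4).

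Most of this stands and limits the size of the point. It does not correct the summary figures, because no SAP rule turns two reductions into days off GBT440. The Medical Director safeguard is also weaker in Part A, where the Sponsor was blinded.

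A reader might infer that the discrepancy between reduction and interruption is larger when the dose is never restored. For example, reductions on Days 8 and 15 without restoration give 28 days, against 14 if dosing stops after Day 14. The documents do not support that comparison. Protocol 8.3.2 describes an interruption as followed by re-initiation and treats discontinuation separately, and SAP 14.1 reports permanent discontinuation on its own line. The gap arises from an earlier last-dose date, (14 − 1) + 1 = 14, and the interruption term is not used. Compliance is 100% on both routes (28/28 and 14/14). The contrast by label alone therefore rests on the restored case in Step 2.

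**Conclusion.** The point holds and is minor. As written, the second reduction in the 600 mg arm gives 0 mg, SAP 14.2 counts the resulting days as exposure, and SAP 9.2 can count them towards its 14 days. In the worked example one subject's exposure is overstated by 7 days as a measure of GBT440 intake, and the arm mean by 0.8 days.

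The dates are assumed and the documents give no expected frequency of reductions, so the number affected may be zero. The effect on the analysis population is narrower still: without restoration it needs a second reduction effective by Day 14, although Protocol 8.3.1 directs every effort to return to the assigned regimen.

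It would be wrong to infer that the primary safety tables are affected. Adverse-event counts and percentages do not use the exposure formula. Nor does the point call for a change to dosing in the remaining study. Protocol 1.5.3 reports safety review of "12 subjects who completed up to 28 days and 16 subjects who completed 15 days of dosing in Part A", so new dosing decisions lie mainly with the 3 planned Part B subjects on 600 mg. The SAP rules apply to all 9.

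**What to change.** Leave the blinded reduction procedure and the CRF-based counts of completion, reductions and interruptions as they are. The second reduction should not be renamed an interruption. That would bring in the Protocol 8.3.2 requirement to restart at the randomized dose, and it would conflict with what a blinded site records.

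- **SAP 14.2:** keep capsule-days for all arms. For the GBT440 arms add two lines: days with at least one active capsule, and cumulative mg. Take reduction and restoration dates from the Study Drug CRF. If the CRF lacks them, use the unblinded pharmacist's dispensing record after unblinding; Protocol 13.1 already lists "pharmacy dispensing records" as source documents.
- **SAP 9.2:** keep the population. Flag any GBT440 subject in it with fewer than 14 active-dose days, and give a sensitivity summary without them.

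The cost is a few lines of SAP text, a little programming and at most 9 dispensing records. The 600 mg exposure figure may look less favourable.

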8.3.2. Dose Interruption

Dose interruption may be initiated by the Investigator based on their assessment of the associated AE severity and overall subject safety and in discussion with the Sponsor's Medical Director.

Re-initiation of dosing will be based on the Investigator's clinical assessment and in discussion with the Sponsor's Medical Director. Dosing should be restarted at the dose assigned to the subject at randomization.

The Investigator must make every effort to restart the dosing regimen assigned to the subject at randomization as soon as it is safe to do so.

Study treatment may be discontinued due to an AE if, in the opinion of the investigator, it is unsafe for the subject to continue receiving study drug. Patients who discontinue study drug should remain in the study and complete all scheduled assessments (refer to [Section 6](#)).

8.3.3. Pirfenidone or Nintedanib Background Therapy

If, in the opinion of the Investigator, the subject experiences significant side effects, judged to be related to pirfenidone or nintedanib therapy, treatment of symptoms and/or dose modifications of these medications are allowed.

The decision to modify pirfenidone or nintedanib dosing is ultimately the responsibility of the investigator. Any modifications to dosing will be managed by the Investigator throughout

the study, taking in to account the Prescriber Information (USPI) of the drugs and past history of care from the subject's IPF health care provider and must be entered into the eCRF.

8.4. Treatment Overdose

To date no events of overdose have been reported. Based on the mechanism of action of GBT440, the result of an overdose might include, but is not limited to, increased severity of previously reported associated adverse events or decreased oxygen delivery to tissues (refer to [Section 1](#)). In the event of a medical emergency due to suspected GBT440 overdose the Medical Monitor should be contacted as soon as possible.

8.5. Concomitant Medications

A concomitant medication is defined as any prescription or over-the-counter preparation, including vitamins and supplements.

In the interests of subject safety and acceptable standards of medical care the Investigator will be permitted to prescribe treatment(s) at his/her discretion. For all randomized subjects, all administered concomitant medications from signing the informed consent until the last study visit must be recorded in the subjects' eCRF.

All prior and concomitant medications that have been reported, will be coded using the current version of the WHO Drug Dictionary.

8.5.1. Permitted therapy

Use of the following therapies is allowed during the study:

- Pirfenidone, nintedanib or N-acetylcysteine (NAC) for the treatment of IPF
 - If at the time of screening, the dose has been stable for at least 1 month prior to screening and with no anticipated need for dose adjustments during the study.
- Corticosteroids:
 - if the dose at screening is ≤ 10 mg per day of prednisone (or an equivalent) and has been stable for at least 2 weeks prior to screening and with no anticipated need for dose adjustments, including reductions in dose, during the study.
 - Use of corticosteroids for other non-IPF related reasons, including but not limited to intra-articular or intramuscular delivery, should be discussed with the medical monitor before administering.
 - Maintenance therapy for other medical conditions listed in the subject's medical history at the time of screening.

Medications such as acetaminophen, non-steroidal anti-inflammatories and routinely taken dietary supplements, including vitamins are allowed at the discretion of the investigator and provided that the medications have no discernable impact on the study.

8.5.2. Restricted Therapies

Subjects should not take the following medications within 14 days prior to screening and during the entire study:

- Strong inducers of CYP3A4/CYP3A5, CYP2B6, CYP2C9 and CYP2C19 (refer to [Appendix B](#); these medications may decrease the blood concentration of GBT440)
- Herbal medications (e.g., St. John’s Wort)

The following medications should be used with caution:

- CYP3A4 substrates with a narrow therapeutic index (refer to [Table 1](#); GBT440 may increase the plasma concentration of these medications)

Table 1 CYP Substrates with Narrow Therapeutic Range

CYP Enzymes	Substrates with Narrow Therapeutic Range
CYP3A4	Alfentanil, astemizole, cisapride, cyclosporine, dihydroergotamine, ergotamine, fentanyl, pimozide, quindine, sirolimus, tacrolimus, terfenadine

Note that this is not an exhaustive list. For an updated listed, see the following link: http://www.fda.gov/Drugs/DevelopmentApprovalProcess/DevelopmentResources/DrugInteractionsLabeling/ucm093664.htm#4
 
Substrates with narrow therapeutic range refers to drugs whose exposure-response relationship indicates that small increases in their exposure levels by the concomitant use of CYP inhibitors may lead to serious safety concerns.
 
Adapted from: FDA DRAFT Guidance for Industry: Drug Interactions Studies-Study Design, Data Analysis, Implications for Dosing, and Labeling Recommendations. February 2012.
	

8.5.3. Therapies for Treatment of IPF

Therapies, other than those used at the time of screening, for the treatment of IPF are not allowed.

If in the opinion of the Investigator an escalation in therapy for IPF is required then study drug should be discontinued and the subject should complete all remaining scheduled assessments (refer to [Section 6.3](#)).

